4.8.4 Haematology, Clinical Chemistry and Renal Function Parameters

The following haematology and clinical chemistry (including renal function) parameters will be summarised.

CONFIDENTIAL

Sponsor:	Zambon S.p.A.	Protocol Number:	Z7224L01
----------	---------------	------------------	----------

Category	Parameter	Unit
Haematology	Haemoglobin	g/L
	Haematocrit	L/L
	Red Cell Count	x10E12/L
	White Cell Count	x10E9/L
	Neutrophils	%
	Total Lymphocytes	%
	Monocytes	%
	Eosinophils	%
	Basophils	%
	Neutrophils (Abs)	x10E9/L
	Total Lymphs (Abs)	x10E9/L
	Monocytes (Abs)	x10E9/L
	Eosinophils (Abs)	x10E9/L
	Basophils (Abs)	x10E9/L
	Platelets	x10E9/L
Chemistry	Sodium	mmol/L
	Potassium	mmol/L
	Chloride	mmol/L
	Uric Acid	mmol/L
	Bilirubin (Total)	umol/L
	Bilirubin (Conj)	umol/L
	AST	U/L
	ALT	U/L
	GGT	U/L
	ALP (Alk Phos)	U/L
	Calcium	mmol/L
	Amylase	U/L
	Renal Function	BUN (Urea)
Creatinine		umol/L

Results as assessed at each applicable visit will be summarised by treatment group and overall using descriptive statistics for continuous variables. Absolute and percentage changes from baseline will also be presented.

A shift table will also be provided presenting results as lower than, within and higher than the central laboratory normal range. This will show the shift from baseline to each post-baseline visit, as well as to the most extreme value (defined as the value furthest outside [below or above] the central laboratory normal range) at any visit after baseline, including unscheduled visits.

Notes:

- Change from baseline for each parameter will be computed using the formula:

$$\text{Change (unit)} = (\text{AVAL [unit]} - \text{baseline AVAL [unit]});$$

CONFIDENTIAL

Sponsor:	Zambon S.p.A.	Protocol Number:	Z7224L01
----------	---------------	------------------	----------

- All results outside the central laboratory normal range will be flagged in the data listings;
- Repeat laboratory results within a visit will replace the original value;
- Due to CTP amendments and to the corresponding changes in the procedures schedule and due to differences in the schedule of assessments in the local versions of the CTP, not all the subjects have undergone the same sequence of laboratory assessments. All the values collected will be summarised jointly. Considering the presence of a stratified and permuted blocks randomisation list, no imbalance between treatments is expected.

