9.1.4. LABORATORY EVALUATIONS

Routine laboratory evaluations will be performed at the Screening Visit (Visit 1), Visit 5 and Visit 7. The haematology and clinical chemistry parameters detailed in Table 1 will be analyzed at the central laboratory using standard, validated laboratory methods.

Renal function will be monitored by laboratory tests (creatinine, Blood Urea Nitrogen [BUN]) performed at the Screening Visit (Visit 1) and during the treatment: at Day 28 of treatment (Visit 3), after 6 months (Visit 5) and at the end of treatment (Visit 7).

Subjects with clinically relevant impaired renal function (as defined by serum creatinine levels ≥ 2.0 x upper limit of normal) will be discontinued.

Note that at Visit 1 and Visit 7 the blood samples for these assessments must be collected after the 12-lead ECG assessments have been performed.

A dipstick urine pregnancy test for women of child-bearing potential will be performed at the investigational site at the Screening Visit (Visit 1) and at all scheduled study visits thereafter.

Female subjects who become pregnant during the trial must be withdrawn from the trial without delay and will be followed up to determine the outcome of the pregnancy. The Investigator is required to inform the Sponsor of a subject's pregnancy and the estimated date of delivery. Reporting requirements are outlined in [Section 16.10](#).

Clinical laboratory tests will be reviewed for results of potential clinical significance before Visit 2 to confirm patient's eligibility and during the trial, as appropriate. Clinically significant laboratory abnormalities arising from Visit 2 onwards are considered to be AEs. Where possible, a diagnosis should be ascribed to the abnormal lab test.

If the Investigator determines a laboratory abnormality to be clinically significant, it constitutes an AE, excluding abnormalities detected at Screening Visit (Visit 1).

Table 1 CLINICAL LABORATORY EVALUATIONS

Hematology: at the Screening Visit (Visit 1), Visit 5 and Visit 7			
Hematocrit	Hemoglobin	Platelet count	Red blood cell count
White blood cell count and differential (neutrophils, lymphocytes, monocytes, eosinophils and basophils)			
Clinical Chemistry at the Screening Visit (Visit 1), Visit 5 and Visit 7			
BUN*	Chloride	AST	
Creatinine*	Uric acid	ALT	
Sodium	Amylase	GGT	
Potassium	ALP	Bilirubin (direct and total)	
Calcium			
Pregnancy Test:			
Urine β -hCG (dipstick) at the Screening Visit (Visit 1) and at all visits thereafter			

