Haematology, clinical chemistry and renal function test results at Visit 1, Visit 5 and Visit 7 will be converted to standard international units and summarised by treatment group using descriptive statistics for continuous variables. Summaries for change from Visit 1 at Visit 5 and Visit 7 will also be provided. Renal function tests will also be summarised at Visit 3. Frequency of subjects with values appearing outside the central laboratory normal range will be reported by visit for each treatment group. All values appearing outside the laboratory normal range will be highlighted in listings.

12-lead Electrocardiogram

Descriptive statistics for ECG results will be presented overall and by treatment.

Adherence and Exposure

Subject adherence will be analysed based on the data collected by the **CCI** logging system.

Adherence will be summarised by treatment group presenting descriptive statistics and percentages of adherent subjects, i.e. with at least 80% adherence.

The total number of doses of IMP taken by each subject, as recorded as part of the **CCI** logging system will be summarised as well.

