Table 14.3.4.5.1.1	Haematology: Results and Change Versus Baseline	(Safety Population)
Table 14.3.4.5.1.2	Haematology: Shift Table	(Safety Population)
Table 14.3.4.5.2.1	Clinical Chemistry: Results and Change Versus Baseline	(Safety Population)
Table 14.3.4.5.2.2	Clinical Chemistry: Shift Table	(Safety Population)
Table 14.3.4.6.1	CC [REDACTED] at Visit 7 (Overall and by Previous Use of Colistimethate Sodium/Colistin)	(Safety Population)
Table 14.3.4.6.2	CC [REDACTED] (Last Available Data) (Overall and by Previous Use of Colistimethate Sodium/Colistin)	(Safety Population)

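### The most-extreme laboratory shift keeps one value per subject across both directions, on an unstated scale, so a subject with both low and high results is counted in one direction only

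*SAP*

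**What the plan says.** SAP 4.8.4 plans one shift table each for haematology and clinical chemistry (renal function included), "presenting results as lower than, within and higher than the central laboratory normal range". It has two parts. The first is by visit: "This will show the shift from baseline to each post-baseline visit". The second is a shift to "the most extreme value (defined as the value furthest outside [below or above] the central laboratory normal range", taken "at any visit after baseline, including unscheduled visits". The SAP gives no scale for that distance and plans no separate rows for the lowest and highest values. The outputs are Tables 14.3.4.5.1.2 ("Haematology: Shift Table") and 14.3.4.5.2.2 in SAP 5.3.4.

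Other displays carry part of the same information:

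- SAP 4.8.4: "All results outside the central laboratory normal range will be flagged in the data listings".
- Protocol 18.4.3: "Frequency of subjects with values appearing outside the central laboratory normal range will be reported by visit for each treatment group".
- Protocol 9.1.4, on sampling: "Routine laboratory evaluations will be performed at the Screening Visit (Visit 1), Visit 5 and Visit 7". Creatinine and BUN are also measured at Visit 3.

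SAP 4.1.11 sets the default for everything else: unless stated otherwise, unscheduled assessments are listed but not analysed. The most-extreme column is the stated exception for the laboratory shifts.

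**The concern.** A single worst value loses nothing when a scale has only one bad end. SAP 4.8.5 to 4.8.7 use such a scale for the clinical assessment of vital signs, for physical examination and for ECG: normal, abnormal not clinically significant, abnormal clinically significant. Sodium, potassium, calcium, white cells, neutrophils and platelets can be abnormal in either direction. For these, one most extreme value makes low and high compete for one cell per subject, and the loser drops out of the column.

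What is at stake is the reading of a safety table. The most-extreme column is the only planned laboratory summary that draws on unscheduled results, so a reader will naturally take ever-low and ever-high counts from it. Also, because the distance scale is not given, two programmers could follow the text faithfully and produce different tables.

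**Working it through.** The documents give no figure on this point, so there is none to reproduce. The check has three steps.

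**1. Which value is kept?** The normal ranges and result pairs below are invented for illustration. For a low value v and a high value h, with limits LLN and ULN, two natural scales are:

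- raw distance: LLN − v against h − ULN
- fold distance: LLN/v − 1 against h/ULN − 1

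(Dividing raw distance by the width of the range changes nothing within a parameter, because both sides are divided by the same number.)

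| Parameter (assumed range) | Low, high | Raw: low v high | Kept | Fold: low v high | Kept |
|---|---|---|---|---|---|
| Potassium (3.5–5.1) | 2.6, 5.4 | 0.9 v 0.3 | low | 0.35 v 0.06 | low |
| Potassium | 2.9, 6.0 | 0.6 v 0.9 | high | 0.21 v 0.18 | low |
| Sodium (135–145) | 120, 148 | 15 v 3 | low | 0.12 v 0.02 | low |
| Neutrophils (2.0–7.5) | 0.4, 8.0 | 1.6 v 0.5 | low | 4.0 v 0.07 | low |
| Neutrophils | 0.4, 9.5 | 1.6 v 2.0 | high | 4.0 v 0.27 | low |
| Platelets (150–400) | 20, 520 | 130 v 120 | low | 6.5 v 0.3 | low |
| Platelets | 20, 560 | 130 v 160 | high | 6.5 v 0.4 | low |

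In every row one abnormal result is dropped. In three of the seven rows the choice of scale decides which one.

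**2. Where can the dropped value still be seen?**

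- Dropped value from a scheduled visit (Visits 5 and 7, plus Visit 3 for renal tests): it is in the by-visit shift and in the flagged listing.
- Dropped value from an unscheduled visit only: SAP 4.1.11 keeps it out of the by-visit shifts, and the most-extreme column has taken the opposite result. It is in the flagged listing but in no laboratory summary table.

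**3. How many subjects could be affected?** Let k be the number of independent post-baseline values, and pL and pH the per-visit chances of a low and a high result.

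- P(ever low) = 1 − (1 − pL)^k
- P(both) = 1 − (1 − pL)^k − (1 − pH)^k + (1 − pL − pH)^k

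Each subject with both loses one direction. If the high is the further value in a share q of them, hidden lows are P(both) × q and hidden highs are P(both) × (1 − q). SAP 3.9 gives 377 randomised, so 377/2 is about 188 per arm. Protocol 9.1.4 gives k = 2 scheduled values; k = 4 allows for two unscheduled ones. All rates are assumptions.

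For example, with k = 2 and pL = pH = 5%: P(both) = 1 − 0.9025 − 0.9025 + 0.81 = 0.005, and 188 × 0.005 = 0.94 subjects.

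| k | pL | pH | Ever low per arm | Both, per arm | Both as share of ever low |
|---|---|---|---|---|---|
| 2 | 1% | 1% | 3.74 | 0.04 | 1.0% |
| 2 | 5% | 5% | 18.33 | 0.94 | 5.1% |
| 2 | 10% | 10% | 35.72 | 3.76 | 10.5% |
| 2 | 5% | 20% | 18.33 | 3.76 | 20.5% |
| 4 | 1% | 1% | 7.41 | 0.22 | 3.0% |
| 4 | 5% | 5% | 34.87 | 5.09 | 14.6% |
| 4 | 5% | 20% | 34.87 | 17.35 | 49.8% |

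The last column is the most that ever-low could be understated (q = 1). At q = 0.5 it halves, and the other half falls on ever-high.

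**The case against.** The best defence is that little is lost. Lows and highs at scheduled visits are counted by arm in the by-visit shifts, and listings flag everything. A post-randomisation abnormality judged clinically significant is also an adverse event under Protocol 9.1.4, and so reaches the tables of SAP 4.8.1. The SAP names no ever-low count, so no planned output is wrong by its own definition. All of this stands, and it is why the point is minor. It does not cover an abnormality at an unscheduled visit that was not reported as an adverse event, and it does not supply the missing scale.

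A reader might also infer stronger things that the documents do not support:

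- **That any high result hides a low of any severity.** The further value wins, in either direction. Even on raw distance, with the assumed ranges, hiding a sodium of 120 needs a result above 145 + 15 = 160, and hiding a platelet count of 50 needs one above 400 + 100 = 500. A high hides every possible low only if it exceeds ULN by more than LLN itself (for neutrophils, above 7.5 + 2.0 = 9.5). Raw distance is itself only one reading, since the SAP names none.
- **That the loss falls on lows alone.** A further low hides a high in the same way.
- **That it biases the comparison of arms through infection-related highs.** Blood sampling is not among the exacerbation-visit assessments in Protocol 8.7, and the flow chart shows none there. A difference by arm is possible, but the documents cannot show one.

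**Conclusion.** The point holds in its narrow form. The rule counts a subject with both low and high results once, in a direction that depends on an undefined distance. Ever-low and ever-high counts taken from the most-extreme column are lower bounds. The only results missing from every laboratory summary table are those seen solely at an unscheduled visit in a subject with a further-out result in the opposite direction.

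The size cannot be derived from the documents. It is probably small: about one subject per arm or fewer with two values and rates up to 5% each way. It grows if highs are common or unscheduled testing is frequent. The illustration assumes independent values and uses randomised rather than treated numbers. Results that repeat in the same direction within a subject would lower the count; swings during acute illness would raise it. This is a low-priority improvement to a descriptive safety display.

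**What to change.** In Tables 14.3.4.5.1.2 and 14.3.4.5.2.2, replace the single most-extreme column with two: shift from baseline to the lowest post-baseline value, and shift from baseline to the highest, each over all scheduled and unscheduled results. Every subject who was ever low or ever high is then counted, and no distance scale is needed.

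SAP Addendum 2.2 records that the database is locked and the study unblinded, so the revised tables should be labelled post hoc, as the SAP Introduction requires. The sponsor has already added and rerun tables at that stage through the Addendum and the later note to file. The cost is one extra column per parameter, a short wording change and slightly longer shift tables.

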4.1.11 Exclusion of Data from the Statistical Analysis

If a subject received the incorrect treatment after being treated with the correct one, all the data collected after the date of the wrong treatment dispensing will be reported in listings and flagged, but not included in the statistical analysis on the IIT, mITT, Safety and PP populations.

CONFIDENTIAL

Sponsor:	Zambon S.p.A.	Protocol Number:	Z7224L01
----------	---------------	------------------	----------

Where not stated differently, assessments conducted at an early termination visit and unscheduled assessments will not be considered in the statistical analysis, but will be listed only.

Only NCFB pulmonary exacerbations with a start date \geq date of first IMP dose and \leq date of treatment completion/discontinuation will be considered in the analysis.

In case of data excluded from the statistical analysis (in the situations described above but also in other cases, for example: spirometry tests excluded due to technical issues, or assessment not done), the derived variables based on these data will not be calculated. For example, the change from baseline to Visit 5 will not be calculated if the measurement at Visit 5 is excluded from the statistical analysis, or all the changes from baseline will not be calculated if the measurements pre-dose are excluded.

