4.1.12 Listings

All data collected will be presented in the listings.

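### SAP 4.8.4 lets a same-visit repeat laboratory result replace a valid original, with no exception for the shift to the most extreme post-baseline value

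*SAP*

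**What the plan says.** SAP 4.8.4 plans by-visit summaries and a shift table in three categories (below, within or above the central laboratory range). The shift runs from baseline to each later visit, "as well as to the most extreme value (defined as the value furthest outside" that range in either direction, and this extreme is taken "at any visit after baseline, including unscheduled visits". That departs from the default in SAP 4.1.11, under which "unscheduled assessments will not be considered in the statistical analysis, but will be listed only" unless another section says otherwise.

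The notes to the same section add: "Repeat laboratory results within a visit will replace the original value". Neither document defines a laboratory repeat, says what prompts one, or says whether it is a re-assay or a fresh sample. No exception is made for the most-extreme shift.

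Protocol 18.4.3 promises: "Frequency of subjects with values appearing outside the central laboratory normal range will be reported by visit for each treatment group". It states no replacement rule. SAP 4.13 does not list the rule among the changes from the protocol, and says that there are no others.

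Three provisions keep the original value in view elsewhere:
- SAP 4.1.12: "All data collected will be presented in the listings".
- SAP 4.8.4: "All results outside the central laboratory normal range will be flagged in the data listings".
- Protocol 9.1.4, except for abnormalities found at screening: "If the Investigator determines a laboratory abnormality to be clinically significant, it constitutes an AE".

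**The concern.** A most-extreme-value table exists so that an abnormal result at any time counts, whatever came later. A replacement rule works against that when the first result was valid and the second was nearer normal. If repeats are prompted by abnormal results, the values removed are the ones the table is meant to show.

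The outcome also depends on a label. The same pair of results contributes both values if the retest is entered as an unscheduled visit, and only the second if it is entered under the same visit.

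Renal function gives this some weight. Protocol 3.1 names renal impairment as a possible effect of high serum concentrations, calls it highly unlikely by inhalation, and plans monitoring. The by-arm laboratory outputs in SAP 5.3.4 are results-and-change tables and shift tables, so the shift tables are where a reader would find out-of-range counts by arm.

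**Working it through.** The plan gives no figure on this point, so there is none to reproduce. The check has three parts.

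**1. Direction.** For one subject and one parameter, let A be all valid post-baseline results and R the results left after replacement. R is a subset of A, so the furthest-out value in R cannot lie further out than the furthest-out value in A. Replacement lowers the extreme or leaves it unchanged.

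Because the table is categorical, a subject's entry changes only if the out-of-range original has a repeat back in range and no other retained post-baseline result is out of range on that side. A repeat that is still out of range on the same side leaves the category as it was.

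**2. One pair of results under two labels** (high original, normal retest)

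| Retest recorded as | By-visit table | Most-extreme shift |
|---|---|---|
| Same visit | Normal | Normal, unless high at another visit |
| Unscheduled visit | High | High |

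Other safety sections do not have this feature. SAP 4.8.5 (vital signs), 4.8.6 (physical examination) and 4.8.7 (ECG) all report a worst post-baseline result with no replacement rule, although Protocol 9.1.6 allows repeat ECG measurements.

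**3. Size, on assumed inputs.** Let q be the share of out-of-range results repeated within the visit, and r the share of those repeats back in range. The documents give neither. The share of out-of-range visit results lost is q × r:

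| q | r = 20% | r = 50% | r = 80% |
|---|---|---|---|
| 0% | 0% | 0% | 0% |
| 10% | 2% | 5% | 8% |
| 25% | 5% | 12.5% | 20% |
| 50% | 10% | 25% | 40% |

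For subjects ever high, a simulation of 400,000 subjects used the three post-baseline renal visits (Visits 3, 5 and 7). It assumed a 5% chance of a high result per visit and a within-subject correlation of 0.5 to 0.9. Each repeat was a fresh draw with the same correlation.

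| Correlation | Ever high, all values | q = 10% | q = 25% | q = 50% |
|---|---|---|---|---|
| 0.5 | 11.75% | 10.99% | 9.77% | 7.64% |
| 0.9 | 7.89% | 7.64% | 7.24% | 6.49% |

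The relative loss, 1 − (after ÷ before), is about 3% to 7% at q = 10%, 8% to 17% at q = 25% and 18% to 35% at q = 50%.

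**The case against.** **Same-visit laboratory repeats may be rare.** Haematology and chemistry go to a central laboratory that reports back to the site (Protocol 9.1.4 and 17.1). A retest prompted by a result would plausibly need a later sample, and could then be recorded as unscheduled and kept. The protocol describes no same-visit laboratory repeat, and a repeat could simply be the re-assay of a faulty sample. This stands as a limit on size. It does not remove the gap, because the rule is written for every repeat and the documents do not say how a later redraw is labelled.

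**The two rules can be programmed together.** One picks the value for a visit and the other takes the extreme across visits. That is true, but the combination no longer gives the worst value observed.

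**The values remain visible.** Listings hold and flag them, and clinically significant ones become adverse events. This stands, and it means that the data are not removed from the report. Listings give no count by arm, however, and adverse-event capture rests on the investigator's judgement, which a normal repeat could influence.

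**Stronger readings.** A reader might infer that every retested abnormal result disappears. The text does not support that: only same-visit repeats replace anything, and only a less extreme repeat matters.

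A reader might also infer that laboratory harm is understated by a material amount, or that a treatment difference is hidden. The documents do not show this. With q = 50% and r = 60% in both arms, assumed rates of 6% and 2% become 6% × 0.7 = 4.2% and 2% × 0.7 = 1.4%. The difference falls from 4.0 to 2.8 points, but the ratio stays at 3. A sustained drug effect would tend to stay abnormal on repeat and so be kept.

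The rule can also act the other way. Laboratory baseline is Visit 1 (SAP 4.1.6), so a repeat there can turn an abnormal baseline normal and add apparent shifts.

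**Conclusion.** The concern holds within narrow bounds. As written, SAP 4.8.4 lets a same-visit repeat displace a valid out-of-range original from the most-extreme shift and from the protocol's by-visit out-of-range frequencies. For the post-baseline extreme the effect runs one way, towards normal or none.

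Its size cannot be determined from the documents. The ranges under the working rest entirely on assumed repeat and normalisation rates, and the loss is zero if no same-visit repeats were taken. The documents support neither a claim that harm was understated nor any single percentage for the loss.

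The tables are descriptive and the primary analysis is unaffected. This is a modest defect in safety reporting that is cheap to correct.

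**What to change.** In SAP 4.8.4:

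1. Define a repeat: re-assay or new sample, and how it is assigned to a visit.
2. Use all valid post-baseline results, superseded originals included, for the most-extreme shift and the out-of-range counts.
3. Leave an original out of these only when its sample is documented as invalid.
4. Keep the replacement rule for by-visit descriptive summaries if wanted. Using the first value there instead would be a preference, not a correction.

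The SAP Addendum (2.2) records that the database is locked and the study unblinded. The haematology and clinical chemistry shift tables (14.3.4.5.1.2 and 14.3.4.5.2.2) should therefore be rerun as labelled post hoc outputs, in line with SAP Section 1, with the number of replaced values reported by arm. That count alone would show whether the point matters in practice.

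The cost is a small derivation change and a rerun of two tables. The later note to file already plans to rerun two efficacy tables to correct a double-counting error, so a limited rerun is feasible.
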